9.2.2.7. Biopsies to Document Disease Recurrence or SPT Following Surgery

Biopsy to obtain histologic or cytologic evidence of CSCC should be attempted in all cases of suspected recurrence or suspected SPT (defined in Section 9.2.2.4) unless biopsy is considered to pose an unacceptable safety risk in the opinion of the investigator (eg, brain lesions). If biopsy of suspected recurrence or suspected SPT is not performed due to unacceptable safety risk associated with biopsy in a particular patient, the reason for not obtaining biopsy will be documented in eCRF. For SPTs, if biopsy is positive for CSCC, surgical removal of the lesion is recommended if possible (unless the biopsy was excisional).

9.2.3. Safety Procedures

9.2.3.1. Vital Signs

Vital signs, including temperature, sitting blood pressure, pulse, and respiration will be collected pre-dose at time points according to [Table 2](#), [Table 3](#), and [Table 4](#).

Note: Blood pressure should be measured after the patient has been resting quietly for at least 5 minutes. Blood pressure may be obtained from a seated or recumbent position and should be done consistently throughout the study. When scheduled at the same time as other procedures, vital signs should be measured prior to clinical laboratory assessments, or exploratory sample collection.

At day 1 of the initial (neoadjuvant) treatment period (Part 1), vital signs will be collected prior to infusion, and approximately 30 minutes after the completion of the infusion. For all other treatment days, vital signs are collected prior to infusion, and approximately 15 minutes after the completion of the infusion. The allowable window for each specified time point is ± 10 minutes.

Weight is recorded at each visit at which vital signs are recorded.

9.2.3.2. Physical Examination

A complete or limited physical examination will be performed at visits specified in [Table 2](#), [Table 3](#), and [Table 4](#). Care should be taken to examine and assess any abnormalities that may be present, as indicated by the patient's medical history.

Complete physical examination will include examination of head and neck, lungs, heart, abdomen, lymph nodes, extremities, and skin. A brief neurologic examination also should be performed.

Limited physical examination will include lungs, heart, abdomen, and skin.

9.2.3.3. Electrocardiogram

A standard 12-lead ECG will be performed at time points according to [Table 2](#).

The patient should be relaxed and in a recumbent or semi-recumbent position at least 5 minutes before recording an ECG. The ECG strips or reports will be retained with the source. The ECG will be reviewed by the investigator (paper or electronic tracing) and will be available for comparison with subsequent ECGs by the investigator. The following will be recorded on the eCRF:

- RR interval (sec)
- PR interval (msec)
- QRS interval (msec)
- QT interval (msec)
- Heart rate (beats per minute; recorded from the ventricular rate)

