- Patients who receive adjuvant radiation therapy or enter observation only during Part 2 of the study will follow a parallel imaging schedule as described in [Section 9.1.6](#).
- The window for treatment visits is ± 3 days. In the event of a missed dose, patients will not be allowed to receive the scheduled cemiplimab dose outside of this window. Any missed doses will result in a reduction in the total number of allowable doses that may be administered.

Table 2: Schedule of Events for Screening, Neoadjuvant Cemiplimab, and Surgery (Part 1 of the Study)

Study Procedure	Screening/ Baseline ¹	Cemiplimab Treatment				Surgery	EOT1 (or Early Termination) ³
		1	22±3	43±3	64±3		
Visit Days	-28 to -1					85 (75 to 100)	30 days ± 10 after surgery
Informed Consent ²	X						
Clinical Assessments							
Medical History/Oncology History	X						
Complete Physical Examination and ECOG PS	X						X
Limited Physical Examination		X	X	X	X		
Vital Signs and Weight	X	X ⁴	X ⁴	X ⁴	X ⁴		X
Height	X						
12-Lead ECG	X						X
Laboratory Tests							
Hematology ⁵	X	X	X	X	X		X
Blood Chemistry ⁵	X	X	X	X	X		X
Pregnancy Test for WOCBP ⁶	X	X	X	X	X		X
Urinalysis	X						X
HBV, HCV, HIV	X						
INR, aPTT ⁷	X					X	
TSH (with reflex T3, free T4) ⁸	X						X
Treatment							
Cemiplimab 350 mg IV Q3W		X	X	X	X		
Surgery ⁹						X	
Response Assessment							
CT/MRI ¹⁰	X			X		X	X
Digital Photography ¹⁰	X			X		X	
Tumor Biopsy ¹¹	X		X				
Treatment Management Plan Assessment ¹²	X				X		
PD/Biomarker Analysis							
PBMC Immune Monitoring Sample		X	X				
Plasma ctDNA Sample	X						X
Whole Blood Genomic DNA (mandatory)	X ¹³						
Whole Blood Genomic DNA (optional sub-study)		X ¹⁴					
Immunogenicity							
ADASample ¹⁵		X				X	X
Patient Reported Outcomes							
EORTC-QLQ-C30 ¹⁶	X					X	

Other Assessments	
Concomitant Medications	← continuous monitoring →
Adverse Events	← continuous monitoring →

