4.5.4. Vital Signs

Vital signs, including temperature, sitting blood pressure, pulse, and respiration will be collected according to the Protocol.

4.5.5. 12-Lead Electrocardiography (ECG)

A standard 12-lead ECG will be performed at time points according to the Protocol. The ECG strips or reports will be retained with the source. The ECG will be reviewed by the investigator (paper or electronic tracing) and will be available for comparison with subsequent ECGs by the investigator: RR interval (sec), PR Interval (msec); QRS Interval (msec); QT Interval (msec); Heart Rate (beat per minute; recorded from the ventricular rate)

Any ECG finding that is judged by the Investigator as a clinically significant change (worsening) compared to the screening value will be considered an AE, recorded, and monitored.

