5.7.4. Analysis of 12-Lead ECG

ECG parameters will be summarized by Baseline and change from Baseline to each scheduled assessment time with descriptive statistics.

ECG status (ie, normal, abnormal, not clinically significant, and abnormal clinically significant) will be reported. Shift tables from baseline to worst post-baseline findings (normal, abnormal not clinically significant, and abnormal clinically significant) during on-treatment period will be generated.

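### The ECG summary uses only uncorrected QT although RR is recorded, so its change from baseline is confounded with heart rate; adding a derived QTcF would fix this at almost no cost (low priority).

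*Protocol*

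**What the plan says.** Protocol 9.2.3.3 has five ECG values recorded on the eCRF: "RR interval (sec"), PR, QRS, "QT interval (msec") and "Heart rate (beats per minute; recorded from the ventricular rate"). SAP 4.5.5 carries the same five: "RR interval (sec), PR Interval (msec); QRS Interval (msec); QT Interval (msec); Heart Rate". Neither document mentions a corrected QT or a correction formula.

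For analysis, SAP 5.7.4 states that "ECG parameters will be summarized by Baseline and change from Baseline to each scheduled assessment time with descriptive statistics". It also reports the rated ECG status (normal, or abnormal with or without clinical significance) and "Shift tables from baseline to worst post-baseline findings" during the on-treatment period.

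The protocol ties ECG timing to Table 2 alone ("A standard 12-lead ECG will be performed at time points according to" that table). Table 2 marks an ECG at screening and at EOT1 or early termination, with EOT1 set at "30 days ± 10 after surgery". Tables 3 and 4 have no ECG row. Protocol 9.1.8 allows unscheduled visits, and SAP 6.4 lets unscheduled measurements count towards abnormal ECG values and worst post-baseline values.

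**The concern.** QT shortens as heart rate rises and lengthens as it falls. A change in raw QT between two ECGs therefore combines a change in repolarization with a change in rate. With QT uncorrected, the numeric summary can show a shift when only the rate has moved, or show none when a rate change has offset a real one.

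Rate could differ between the two scheduled ECGs: one precedes treatment and the other follows neoadjuvant dosing and surgery. Protocol 3.3.2 also reports hypothyroidism as a treatment-related event in 6.6% of the pooled cemiplimab population, and thyroid function affects heart rate. The documents do not say how large any shift would be.

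What is at stake is whether one descriptive safety output can be interpreted. Protocol 5.3 names ECG results as a safety variable, and Protocol 8.3.3.1 lists cardiac events among the less common immune-related events.

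**Working it through.** The plan states no QT or QTc figure, so there is none to reproduce. The check has two parts.

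**1. Size of the heart-rate effect**

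Assumed inputs (the documents give none): baseline QT 380, 400 or 420 msec; baseline heart rate (HR) 70 bpm; changes of 5 to 20 bpm.

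Formulas: RR = 60/HR in seconds; QTcF = QT/RR^(1/3). If QTcF is constant, the change in raw QT is QT × [(HR0/HR1)^(1/3) − 1].

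With baseline QT 400 msec at 70 bpm, RR = 0.857 s and QTcF = 421.1 msec.

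- **Rate rises to 80, QTcF constant:** (70/80)^(1/3) − 1 = −4.35%, so raw QT changes by −17.4 msec. This is apparent shortening.
- **Rate falls to 60, QTcF constant:** (70/60)^(1/3) − 1 = +5.27%, so raw QT changes by +21.1 msec. This is apparent prolongation.
- **Rate rises to 80, raw QT stays at 400:** QTcF = 400/0.75^(1/3) = 440.3 msec. The raw QT change is 0 while QTcF rises by 19.2 msec.

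Range over baseline QT 380 to 420 msec, QTcF constant:

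| Heart-rate change from 70 bpm | Change in raw QT (msec) |
|---|---|
| +5 | −8.6 to −9.5 |
| +10 | −16.5 to −18.3 |
| +20 | −30.5 to −33.8 |
| −10 | +20.0 to +22.1 |

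Under the Bazett correction, QT/RR^(1/2), the 10 bpm shifts are larger: −24.5 to −27.1 msec for a rise and +30.4 to +33.7 msec for a fall. The conclusion does not depend on the choice of correction.

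**2. Timing of the scheduled post-baseline ECG**

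Inputs: surgery nominally day 85, window day 75 to 100 (Table 2); EOT1 30 ± 10 days later; dose 4 on day 64 ± 3 (Protocol 6.1.2).

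- Nominal: 85 + 30 = day 115, which is 115 − 64 = 51 days after dose 4.
- Earliest: 75 + 20 = day 95. Latest: 100 + 40 = day 140.
- Interval after dose 4: from 95 − 67 = 28 to 140 − 61 = 79 days.

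After four doses this lies inside the 90-day on-treatment window of SAP 4.5. If dosing stops early and surgery still falls in its window, the interval is 49 to 100 days after dose 3 and 70 to 121 days after dose 2, so the ECG can fall outside. Unless an unscheduled ECG is done, the worst post-baseline value is a single reading.

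**The case against.** The case against giving this weight is good, and most of it stands.

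- **Other outputs give partial protection.** RR and heart rate are among the summarized parameters, so a mean rate shift would be visible beside the QT result. The investigator reviews each tracing, the rated status goes into shift tables, and SAP 4.5.5 makes a clinically significant worsening from screening an AE. A reader might infer that a real prolongation would simply go unreported; the documents do not support that. What remains is that separate summaries of QT and rate cannot give a corrected value for each patient, and the shift table rests on a rating, not a corrected interval.
- **The mean may move little.** Opposite individual rate changes largely cancel in a mean, and Protocol 9.2.3.3 standardizes posture and rest. Nothing in the documents points to a mean shift of 10 bpm. But SAP 5 also reports the standard deviation, quartiles, minimum and maximum, where individual rate changes do not cancel.
- **EOT1 is not the only possible post-baseline ECG.** A reader might infer this from Table 2. It is the only scheduled one, its column also serves early termination, and unscheduled ECGs may be used.
- **Correction does not cure timing.** QTcF from one reading 28 to 79 days after dose 4 still says little about effects during dosing.
- **No trial conclusion depends on it.** The safety endpoint in Protocol 4.2 is AEs, SAEs, deaths and laboratory abnormalities. Protocol 11.5.5.2 plans no ECG summary, and QT is not among the risks in Protocol 3.3.2.
- **No data are lost.** QT and RR are both recorded, so QTcF can be derived at any time. That is also why specifying it before database lock is easy.

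**Conclusion.** The point holds as a low-priority improvement. The planned numeric QT summary is uncorrected in both documents and therefore confounded with heart rate. Under the assumed baseline (QT 380 to 420 msec at 70 bpm), a 10 bpm change moves raw QT by about 17 to 22 msec with no change in QTcF. The direction follows from the formula; the size rests on these assumed values and on the Fridericia correction. The rate shift that will occur in this trial is unknown.

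The finding goes no further than that summary. The documents do not show that an effect would be missed overall, and the pCR analysis is untouched. Nor does the finding justify removing uncorrected QT, which is a listed protocol variable: the corrected value belongs beside it.

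**What to change.** In SAP 4.5.5, add a derived variable QTcF = QT/RR^(1/3), with RR in seconds, calculated for each ECG from the recorded QT and RR.

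In SAP 5.7.4, summarize QTcF at baseline and as change from baseline alongside the five listed parameters. Add counts of patients by category of QTcF value and of QTcF change, at thresholds that the sponsor chooses and states before database lock.

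The cost is one derived variable and a short SAP addition. No new data, visits or eCRF fields are needed. The ECG schedule stays as it is, so the report should state that the scheduled post-baseline value is a single reading taken after surgery or at early termination.

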9.2.3.4. ECOG Performance Status

ECOG performance status will be performed at the time points according to [Table 2](#), [Table 3](#), and [Table 4](#). Performance status will be assessed according to ECOG criteria in [Appendix 1](#).

9.2.3.5. Laboratory Testing

Hematology, blood chemistry, urinalysis, and pregnancy testing samples will be collected at time points according to [Table 2](#), [Table 3](#), and [Table 4](#).

Detailed instructions for sample collection and shipment of samples are in the laboratory manual provided to study sites.

Unless otherwise specified, all laboratory tests will be performed by local labs.

Blood Chemistry

Sodium	Total protein, serum
Potassium	Creatinine
Chloride	Blood urea nitrogen (BUN)*
Carbon dioxide (bicarbonate)**	Aspartate aminotransferase (AST)
Calcium	Alanine aminotransferase (ALT)
Glucose (fasting or non-fasting)	Alkaline phosphatase
Albumin	Total bilirubin

*At ex-US centers at which a urea assays are performed instead of BUN; the urea assay will be acceptable.

**At ex-US centers at which the bicarbonate assay is not performed as part of the routine chemistry panel, it may be omitted.

Hematology

Hemoglobin	Differential:
White blood cells	Neutrophils
Platelet count	Lymphocytes
	Monocytes

Urinalysis

pH	Glucose
Specific gravity	Blood
Ketones	Spot urine protein

Other Laboratory Tests

- HBV, HCV, HIV testing
- Pregnancy test: Serum β -HCG or urine β -HCG
- Thyroid-stimulating hormone (TSH) with reflex T3 and free T4 will be analyzed by the site's local laboratory. If TSH is abnormal, a T3 and free T4 should be measured by the site's local laboratory. Coagulation will be assessed at screening and prior to surgery using measurements of INR and aPTT.

Abnormal Laboratory Values and Laboratory Adverse Events

All laboratory values must be reviewed by the investigator or authorized designee.

Significantly abnormal test results that occur after start of treatment must be repeated to confirm the nature and degree of the abnormality. When necessary, appropriate ancillary investigations should be initiated. If the abnormality fails to resolve or cannot be explained by events or conditions unrelated to the study drug or its administration, the Medical/Study Director must be consulted.

The clinical significance of an abnormal test value, within the context of the disease under study, must be determined by the investigator.

Criteria for reporting laboratory values as an AE are provided in Section [10.4.5](#).

9.2.4. Survival Data Collection

Every effort will be made to collect survival data on all patients, including patients who withdraw from the study for any reason but have not withdrawn consent to collect survival information. If the death of a patient is not reported, the date of the last patient contact in this study will be used in the determination of the patient's last known date of alive.

9.2.5. Anti-Drug Antibody and Pharmacokinetic Procedures

Blood samples will be taken to measure ADA as part of safety assessment at the individual patient level. When appropriate, cemiplimab concentration may also be measured using these blood samples.

9.2.5.1. Anti-Drug Antibody Measurements and Samples

Anti-drug antibody samples for cemiplimab immunogenicity assessments will be collected at visits and time points listed in [Table 2](#), [Table 3](#), and [Table 4](#). The actual time of each blood draw must be recorded. Pre-infusion is defined as before the start of subsequent cemiplimab infusions.

Any unused samples collected for immunogenicity assessments may be used for exploratory biomarker research.

9.2.5.2. Drug Concentration Measurements and Samples

Cemiplimab concentrations in the serum may be measured using samples collected for ADA analysis, if appropriate as part of safety assessment at the individual patient level. Concentrations will be measured using a validated enzyme-linked immunosorbent assay method.

9.2.6. Exploratory Pharmacodynamic and Biomarker Procedures

Samples for exploratory pharmacodynamic and biomarker analysis will be collected according to the time points listed in the schedules of events ([Table 2](#), [Table 3](#), and [Table 4](#)).

Analysis of PD-L1 expression levels (determined by immunohistochemistry [IHC]) and TMB in pretreatment tumor samples will be prioritized over other exploratory tumor assessments. These analyses may provide a better understanding of PD-L1 expression level and TMB as potential predictive biomarkers of the efficacy of cemiplimab. These exploratory analyses will not be included in the CSR.

After completion of PD-L1 expression and TMB analysis, the remaining tumor tissue and/or other samples sources (eg, peripheral blood) may be used to study other candidate biomarkers associated with efficacy of cemiplimab, including assessment of circulating tumor deoxyribonucleic acid (ctDNA) as a potential predictor of disease recurrence, characterization of expression of other immune-related or CSCC cancer-related genes (DNA, RNA and/or protein), tumor-infiltrating lymphocytes and other immune cell populations, HPV (human papillomavirus) status and subtype, human leukocyte antigen variants and antigen processing components, and T cell receptor repertoire.

Methodologies that may be employed include, but are not limited to, IHC, multiple IHC, RNA sequencing, RNAscope[®], fluorescence in situ hybridization, flow cytometry, and whole exome DNA sequencing. Candidate biomarker analysis will also be performed in pretreatment and posttreatment blood samples (serum, plasma, Peripheral blood mononuclear cells [PBMC], and/or whole blood) and, if available, samples from SPTs and recurrent disease lesions.

9.2.6.1. Tumor Biopsy

For all study patients, a pretreatment tumor sample (preferably an FFPE tissue block, or alternatively, 25 unstained FFPE slides) should be obtained. The sample should be provided to the central lab in the screening period, but a patient's enrollment would not be delayed if sample is not received in screening period. When possible, tumor sample (FFPE block or 25 unstained FFPE slides) should be provided when there is histologic sampling (biopsy or surgical removal) of SPT or recurrent CSCC lesion (see Section 9.2.2.4 and Section 9.2.2.7). Complete instructions on the collection, processing, handling, and shipment of all samples will be provided in the laboratory manual.

Any available, FFPE biopsy tissue from samples collected at time points according to Table 2, Table 3, and Table 4, as well as archival specimens from previous treatment, in addition to clinical diagnostic uses, will be utilized for biomarker assays. Specifically, these samples will be assessed using immunohistochemistry (to measure PD-L1 expression) and using whole exome sequencing (to measure tumor mutation burden).

If sufficient sample is available, tumor tissue samples will also be subjected to multiplex immunohistochemistry as a measure of tumor infiltration of immune cells, gene expression profiling (using RNA sequencing, RNAscope[®], fluorescence in situ hybridization, or other methods) as a measure of composite tumor microenvironmental phenotype, and targeted study of gene variants (tumor mutations) such as those affecting DNA repair pathways. They may also be profiled using next-generation sequencing for the T cell receptor repertoire, as a measure of tumor-associated T cell clonal proliferation.

If biopsy is considered by the investigator to pose an unacceptable safety risk to the patient or would compromise tumor measurements, biopsy may be waived for an individual patient (see Table 2 and Section 9.2.2.7).

9.2.6.2. Circulating Tumor DNA

Tumor mutations (known oncogenic drivers, as well as indicators of overall mutational load) are a measure of tumor aggressiveness and growth potential, residual disease, and altered tumor evolution under the selective pressures of therapy. Such analyses are exploratory methods for evaluating treatment response, as well as potential predictive markers of longer-term efficacy. Mutations will be measured in DNA isolated from plasma samples collected at time points indicated in the schedule of events (Table 2, Table 3, and Table 4). Modulation of mutations pertaining to tumor cell function, genomic landscape, and immunogenicity all constitute exploratory measures.

9.2.6.3. Peripheral Blood Mononuclear Cells for Exploratory Immune Monitoring

Proteins expressed on the surface of immune cells serve as markers of the lineage, functionality, and activation state of those cells, and help to characterize the cell population. Expressed protein markers of lineage and activation trajectories will be measured by quantitative flow cytometry. Anti-tumor functionality in a T cell population is characterized by the combination of tumor antigen specificity (associated with the somatically recombined, clonally identifying T cell receptor sequence) and phenotypic properties indicative of function (measurable through both RNA and protein expression). T cell activity, tumor antigen specificity, the T cell receptor (TCR) repertoire sequences, and other measures of the anti-tumor immune response will be measured through 1) functional assay of PBMC samples collected at time points indicated in the schedule of events (Table 2) followed by 2) molecular profiling including but not limited to high-throughput RNA sequencing or reverse transcriptase polymerase chain reaction (RT-PCR).

9.2.6.4. Whole Blood for DNA Analysis (Mandatory Sample)

A whole blood genomic DNA sample will be collected during screening as indicated in the schedule of events (Table 2). Whole exome sequencing of germline blood DNA will be performed, and data will be used as a reference for tumor DNA sequencing analysis to distinguish germline from somatic tumor gene variants. This sample will not be used for other research purposes.

9.2.7. Genomics Sub-study (Optional Sample)

Patients who agree to participate in the genomics sub-study will be required to sign a separate genomics sub-study ICF before collection of the samples. Whole blood samples for DNA and RNA extraction should be collected on day 1/baseline (predose) but may be collected at any study visit. DNA and RNA samples for the genomics sub-study will be single-coded as defined by the International Council for Harmonisation (ICH) guideline E15. Sub-study samples will be stored for up to 15 years after the final date of the database lock and may be used for research purposes. If there are specific site or country requirements involving the pharmacogenomic analyses which the sponsor is unable to comply with, samples will not be collected at those sites.

The purpose of the genomic analyses is to identify genomic associations with clinical or biomarker response, other clinical outcome measures and possible AEs. In addition, associations between genomic variants and prognosis or progression as well as related diseases may also be studied. These data may be used or combined with data collected from other studies to identify and validate genomic markers related to the study drug and related diseases.

Analyses may include sequence determination or single nucleotide polymorphism studies of candidate genes and surrounding genomic regions. Other methods, including whole-exome sequencing, whole-genome sequencing, DNA copy number variation, and transcriptome sequencing may also be performed. The list of methods may be expanded to include novel methodologies that may be developed during the course of this study or sample storage period. Results from the genomic sub-study will not be reported in the CSR.

